8.2.3. Secondary outcomes

The primary outcome (STAI score) will be tested for correlation against imaging and surfaceguided data collected for participants.

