4.2. Secondary outcomes measures

4.2.1. Imaging Data

Imaging data, to include the treatment setup shifts determined by either two-dimensional (kV planar) or three-dimensional cone-beam CT (CBCT) imaging.

Surface-guided radiotherapy (SGRT) data analysis from the AlignRT system will include the variability of patient movement via the real-time deltas (RTDs). Additional metrics available for analysis are not currently known and will be explored.

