4.4. Table of endpoints/outcomes

Table 1: Study objectives and outcome measures

Objectives	Outcome Measures	Timepoint(s) of evaluation of this outcome measure (if applicable)
Primary Objective To determine whether an additional patient consultation with a medical physicist lowers patient- reported anxiety.	Short form of state scale of Spielberger State-Trait Anxiety Inventory (STAI), administered at patient recruitment (baseline), after patient first treatment, and after patient final treatment.	Three timepoints: recruitment, before first and last treatment
Secondary Objective To determine whether patient set-up errors or SGRT data correlate with patient- reported anxiety.	Magnitude of setup errors (determines by 2D or 3D imaging), variability of SGRT real time deltas (RTDs) and correlation with patient-reported anxiety	Two timepoints: first and last treatment
Tertiary / Exploratory Objectives Technical satisfaction	Two technical satisfaction questions on a 5-point Likert scale. Comparison between groups and additional questions examining patient information needs.	One timepoint: before first treatment
Sub-group analysis	Variation/correlation of patient- reported anxiety and demographic information	Three timepoints: recruitment, before first and last treatment
Comparisons at each timepoint	Patient anxiety – longitudinal analysis of anxiety and comparison of proportion of high and low anxiety patients, including analysis by treatment length/duration.	Three timepoints: recruitment, before first and last treatment
Treatment adherence	Treatment attendance adherence, defined as 1 – [(number of	Every treatment fraction (varying on an individual patient basis)

	treatment days missed) / (total prescribed treatment fractions)]	
	Bladder filling adherence, defined as the difference in bladder volume daily compared to planned volume.	
Health-related Quality of Life (HRQoL)	Correlation of EQ-5D-5L scores with STAI and demographics. Change in HRQoL with intervention vs control	Three time points: recruitment, before first and last treatment

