5. PARTICIPANT ELIGIBILITY CRITERIA

5.1. Inclusion Criteria

- Referred for radical radiotherapy at the Robert White Radiotherapy Centre (RWRC)
- Histological or radiological diagnosis of cancer, or appropriate referral for benign condition
- Provision of informed consent to participate.

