6.3. Randomisation

Following completion of baseline information collection, a member of the research team will randomise the participant to one of the two treatment arms: physicist consultation or standard of care.

Patients will be randomised in order to minimise systematic bias, using a secure web-based system Sealed Envelope (https://www.sealedenvelope.com/simple- randomiser/v1/trials/rapport), certified as meeting ISO/IEC 27001 standards and the NHS England Data Security and Protection Toolkit.

Participants will be allocated to intervention group or to the control group in a 1:1 ratio. Randomisation will be stratified by gender. This is a surrogate for treatment site: the most common radiotherapy treatment sites (particularly at RWRC) are breast and prostate cancer. However, to ensure approximately equal distribution of treatment sites in each arm and avoid problems of low numbers of less common treatment sites, gender has been chosen has the stratification criteria. It is acknowledged that with the low sample size required in this study, distribution is likely still to be unequal but there is little evidence that the primary outcome varies by gender.

Upon randomisation, each participant will be assigned a unique Trial Number which will be used as the principal identifier on trial data collection forms and questionnaires. The research team member will disclose the allocation to the participant and will ensure the allocation is followed as described below.

6.4. **Provision of Treatment**

Following allocation, the participant will be informed of which trial arm they have been randomised to. Where required, the consultation will be booked by the PI or delegate and the patient informed what time this will be (as it will not be on their routine appointment list given at the CT appointment). If possible, a reminder will be sent via the DoctorDoctor service.

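### The secondary outcome names only an unadjusted correlation of STAI with set-up and surface data across mixed sites and imaging modes, which can dilute a real within-site association

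*Protocol*

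**What the plan says.** Section 8.2.3 is a single sentence: "The primary outcome (STAI score) will be tested for correlation against imaging and" surface-guided data. It names no covariate, coefficient or unit of analysis.

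Table 1 (4.4) defines the outcome as "Magnitude of setup errors (determines by 2D or 3D imaging), variability of SGRT real time deltas (RTDs) and correlation with patient-reported anxiety", evaluated at "Two timepoints: first and last treatment". Section 4.2.1 says the shifts are those "determined by either two-dimensional (kV planar) or three-dimensional cone-beam CT (CBCT) imaging". For surface guidance it names the variability of the real-time deltas and adds: "Additional metrics available for analysis are not currently known and will be explored".

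Section 5.1 admits any radical treatment site. Section 6.3 states that "the most common radiotherapy treatment sites (particularly at RWRC) are breast and prostate cancer" and uses gender as the stratification factor in place of site. The same section says there is little evidence that the primary outcome varies by gender.

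Section 6.2.2 records treatment site and motion management such as breath-hold. Section 6.6 collects 2D shifts, cone-beam CT shifts and surface data. Section 3.2 stratifies analysis by education, health literacy and other sociodemographic data, without naming treatment site. Section 8.2.2 does name covariates, but for the primary outcome. The Background (section 1) expects the effect of anxiety on movement to matter most for regions affected by breathing, breath-hold treatments included.

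**The concern.** Set-up shift size can differ between body sites, and a shift magnitude from planar imaging is not necessarily on the same scale as one from cone-beam CT. An unadjusted correlation counts these differences as part of the spread in shift size. That spread has nothing to do with anxiety, so it shrinks the coefficient and lowers power. This happens even when anxiety is the same at every site.

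The trial wants to corroborate or refute an earlier report that anxiety and set-up error are linked. A weak or null result from a diluted correlation would be hard to interpret: it could mean no association, or one hidden by site mix. The protocol itself expects region and breath-hold to matter and already collects them, so leaving them without a role gives up information that is in hand.

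**Working it through.** **Inputs from the protocol.** SD 13, difference 10, two-sided 0.05, 80% power, 54 patients recruited as 60 (8.1); intercept SD 11.31 and residual SD 2.57 (Appendix 1).

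**Assumed inputs, not in the protocol.** Two site groups of equal size; the between-site gaps in shift and in STAI; the within-patient correlation (ICC) of set-up error; equal error per axis for 2D and 3D imaging.

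**1. The stated sample size.** n per arm = 2 × (1.96 + 0.8416)² × 13² / 10² = 26.5, so 27 per arm and 54 in total; 54 / 0.9 = 60. Both figures reproduce. The protocol gives no figure for the correlation. With 54 patients and one value each, the correlation detectable with 80% power is tanh(2.80 / √51) = 0.373.

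**2. Dilution when STAI does not differ by site.** Let the within-site correlation be r and the gap in mean shift be d within-site SDs. With equal groups, the between-site gap adds d²/4 to a within-site shift variance of 1, and the covariance with STAI is unchanged. So overall r = r_within / √(1 + d²/4). Power is simulated at N = 54 with r_within = 0.373.

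| Gap d (assumed) | √(1 + d²/4) | Overall r | Power, unadjusted | Power, site-adjusted |
|---|---|---|---|---|
| 0 | 1.000 | 0.37 | about 80% | about 80% |
| 1.0 | 1.118 | 0.33 | about 71% | about 80% |
| 1.5 | 1.250 | 0.30 | about 60% | about 80% |
| 2.0 | 1.414 | 0.26 | about 49% | about 80% |

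**3. Imaging mode.** Suppose 2D gives two axes and cone-beam CT three, with equal error σ per axis, and magnitude means vector length. The mean lengths are 1.253σ and 1.596σ, a ratio of 1.27. The SDs are √(2 − π/2) = 0.655σ and √(3 − 8/π) = 0.673σ, so the gap is 0.343 / 0.664 = 0.52 SD. In an equal mix this alone takes r from 0.373 to 0.373 / √(1 + 0.52²/4) = 0.36. That is small by itself, but it adds to the site effect where mode follows site.

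**4. Spurious association, only if STAI also differs by site.** With no within-site association and gaps a (STAI) and d (shift) in SD units, r = 0.25ad / √[(1 + 0.25a²)(1 + 0.25d²)]. False-positive rates are simulated with one visit per patient.

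| a, d (assumed) | Spurious r | False-positive rate |
|---|---|---|
| 0, 1.5 | 0 | 0.049 |
| 0.3, 0.5 | 0.04 | 0.056 |
| 0.5, 0.5 | 0.06 | 0.073 |
| 0.5, 1.0 | 0.11 | 0.119 |
| 0.5, 1.5 | 0.15 (simulated 0.14) | 0.177 |

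With site adjustment and one value per patient the rate is 0.048 to 0.053 throughout.

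**5. Two visits, only if pooled as independent rows.** With no random slope, Appendix 1 gives an STAI correlation between visits of 11.31² / (11.31² + 2.57²) = 0.95. Allowing the slope SDs considered there gives 0.92 to 0.94. The variance inflation is 1 + 0.93 × ICC of set-up error. For ICCs of 0, 0.3, 0.5 and 0.8 it is 1.00, 1.28, 1.47 and 1.74. The type I error is 2 × [1 − Φ(1.96 / √inflation)] = 0.050, 0.083, 0.105 and 0.138 (simulated 0.080, 0.104 and 0.145 for the last three).

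**The case against.** The strongest reply is that the protocol promises a detailed analysis plan, signed off before any analysis (8.2), and that covariates and the unit of analysis are commonly left to it. That holds for much of the detail. It does not remove the point, because the protocol does name a method. That method is unadjusted, and the outcome accepts either imaging mode as one magnitude.

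Three stronger readings are tempting, and the documents do not support them.

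- A reader might infer that the two visits will be pooled and the confidence limits will be too narrow. The protocol never says so. The two timepoints in Table 1 fit separate correlations per visit, which have no repeated-measures problem. Even pooled, the error is correct if set-up error is uncorrelated within patients.
- A reader might infer that the correlation will be spuriously positive because breast and prostate patients differ in anxiety. Section 6.3 says there is little evidence that STAI varies by gender, its surrogate for site. If STAI does not differ by site, the spurious correlation is zero.
- A reader might infer that the surface-guidance measure is wholly open. Variability of the real-time deltas is named in the trial summary, in 4.2.1 and in Table 1. Only its summary statistic and any additional metrics are unspecified.

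It is also fair that the between-site gaps are assumptions, and that small gaps do little. Section 6.3 warns of low numbers at less common sites, which argues against fine site categories.

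**Conclusion.** The point holds in a limited form. The only method named for the secondary outcome ignores treatment site and imaging mode, and following it would weaken a true within-site association. For assumed site gaps in shift of 1 to 2 SD, a correlation of 0.37 becomes 0.33-0.26 and power at 54 patients drops from 80% to about 71-49%. This needs no difference in anxiety between sites. It does rest on the assumed gaps and on an equal split between two site groups; with little difference in shift between sites the loss is small.

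Two further risks are conditional. A spurious association needs STAI to differ by site as well. A type I error of about 8-14% needs the visits to be pooled as independent rows and set-up ICCs of 0.3-0.8. The primary comparison is unaffected. The change is worth making because the data are already collected and the cost is low.

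**What to change.** In 8.2.3, or in the analysis plan with a pointer from 8.2.3, replace the plain correlation with a regression or partial correlation of shift magnitude on STAI at the same visit. Adjust it for treatment site in broad groups (breast, prostate, other) and for imaging mode. Do the same for real-time-delta variability, with site adjustment and one summary statistic named in advance. State what role, if any, breath-hold has.

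Either analyse each visit separately or, if both are combined, include a random intercept per patient. Report the adjusted slope or partial correlation with its 95% confidence interval. Label any additional surface-guidance metrics exploratory.

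The cost is two degrees of freedom for three site groups, one for imaging mode, and slightly more analysis work. No new data are needed (6.2.2, 6.6). Broad site groups keep the model workable with about 54 patients, at the price of some residual spread within the 'other' group.

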8.2.4. Exploratory outcomes

The exploratory outcomes will not be tested for statistical significance. Correlation with group anxiety scores will be tested against:

- a. Technical satisfaction
- b. Patient information needs
- c. Treatment adherence (appointment attendance and bladder filling)

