2.2.2. Secondary objectives

- To determine whether the magnitude of patient set-up errors correlate with patient-reported anxiety.
- To determine whether data reported by SGRT (such as surface variability) correlate with patient-reported anxiety.
- To determine whether there is a difference in technical satisfaction between the intervention and control arms.
- To determine if treatment adherence (attendance, treatment preparation such as bladder filling) is influenced by having more technical information.
- To collate patient questions and report common themes
- To explore patient experiences, including their interest in physicist consultations as a clinical service, and their information requirements.
- To determine the staff time requirement for physicist consultations

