6.5. Start of treatment

When patients start treatment, they will be asked to complete a questionnaire on the day of their first treatment. Ideally this will be completed before the treatment appointment, otherwise it must be completed after the treatment appointment and on the day of first treatment. This is due to some patients having very short treatment regimens. Patients will be provided with a questionnaire packet to be completed, and a member of the research team will complete a case report form (CRF). The start of treatment data collected (either participant-reported or medical records) will be:

- Patient-reported anxiety STAIS6 questionnaire
- EQ-5D-5L questionnaire

- Technical satisfaction questions
- Clinical information collected from medical records
 - Scheduled number of treatment fractions (this can change between referral and prescribing by Oncologist)
 - Does the patient have bladder filling/preparation. If so, baseline volume and details from planning CT
- Intervention information (where applicable):
 - Physicist conducting consultation.
 - Consultation duration.
 - Discussion points and patient questions analysis of themes and topics will be conducted.

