8.4. Economic evaluation

A criticism of utilising physicist-time for direct patient care is the cost and time involved for, often, highly paid and specialised technical staff. This study will collect data on the time spent preparing and conducting patient consultations to inform future cost-effectiveness studies.

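### Section 8.2.4 plans only correlations with anxiety for technical satisfaction and adherence, which does not match the between-arm objectives, and Section 6 omits the preparation time promised in 8.4

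*Protocol*

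**What the plan says.** Section 2.2.2 lists seven secondary objectives. Three matter here:

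- "To determine whether there is a difference in technical satisfaction between the intervention and control arms".
- Whether adherence "is influenced by having more technical information".
- "To determine the staff time requirement for physicist consultations".

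Sections 4.3.1 and 4.3.4 and Table 1 (Section 4.4) treat satisfaction and adherence as exploratory. For satisfaction, Table 1 names a group comparison, evaluated before first treatment. For adherence, Table 1 defines an attendance measure and a bladder-volume measure but names no comparison of arms. For quality of life, it names correlations of EQ-5D-5L with STAI and demographics, and "Change in HRQoL with intervention vs control".

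Section 8.2 defers detail to a statistical analysis plan and says in general terms that data are analysed according to intervention group. Section 8.2.4 then gives the analysis of the exploratory outcomes: "The exploratory outcomes will not be tested for statistical significance. Correlation with group anxiety scores will be tested against" technical satisfaction, information needs and adherence. EQ-5D-5L is not in that list.

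On staff time, 8.4 states: "This study will collect data on the time spent preparing and conducting patient consultations". The intervention items in 6.5 are the physicist's identity, "Consultation duration", and the discussion points and questions. Section 9.2 refers the reader to Section 6 for everything collected.

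**The concern.** The objectives ask what the consultation does to satisfaction and adherence. The analysis section asks how those outcomes vary with anxiety. Randomisation protects the first question but not the second: patients who are less anxious may be more satisfied or attend better for reasons unrelated to the consultation. An analyst who followed 8.2.4 literally would report associations and leave the two objectives without an estimate.

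In addition, consecutive sentences of 8.2.4 say that these outcomes will not be tested for significance and that a correlation will be tested. Whoever writes the analysis plan must decide which sentence governs.

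The staff-time point is of a different kind because it concerns collection. If site staff work from Section 6, preparation time is not recorded, and no later analysis plan can supply it.

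**Working it through.** No figure in the protocol bears on this point, so the check sets the passages side by side.

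| Item | Objective in 2.2.2 | Section 4 and Table 1 | Section 8 | Section 6 |
|---|---|---|---|---|
| Technical satisfaction | Difference between arms | Group comparison | Correlation with anxiety | Baseline, first and last treatment |
| Adherence | Effect of more information | Measures defined, no arm comparison | Correlation with anxiety | Bladder data where applicable |
| HRQoL (EQ-5D-5L) | Not listed | Change by arm; correlations | Not listed in 8.2.4 | Baseline, first and last treatment |
| Staff time | Time required | Not listed | 8.4: preparing and conducting | 6.5: duration only |

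**Can the correlation stand in for the arm comparison?** The arm effect is mean(Y, consultation) − mean(Y, control). The correlation is cov(Y, A) / (SD of Y × SD of A), where A is the anxiety score; arm does not enter it. Computing the correlation within each arm does not help. Adding a constant to every satisfaction score in one arm changes the arm effect by that constant and leaves both within-arm correlations unchanged.

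A simulation on assumed values illustrates this. It uses 27 patients per arm (the number in 8.1 before over-recruitment), normal outcomes and 5,000 runs. It compares a two-sample t-test with a Pearson correlation, each at 0.05. Significance serves here only as a measure of what each analysis can see.

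| Assumed truth | Arm comparison significant | Correlation with anxiety significant |
|---|---|---|
| Satisfaction shifted by 0.8 SD in one arm, unrelated to anxiety | 82.6% | 5.1% |
| No arm effect, correlation of −0.5 with anxiety | 4.1% | 97.3% |

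In the first case the correlation misses a real effect of the consultation. In the second it is nearly always significant although the consultation does nothing to satisfaction.

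**Staff time.** Let p be preparation time and c consultation time. The requirement is p + c, the Section 6 list yields c, and the share missed is p / (p + c). The Trial Summary gives c as 20–30 minutes. The protocol gives no value for p, so the share cannot be calculated from it.

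**Count.** Of the seven objectives in 2.2.2, two (satisfaction, adherence) have an analysis in 8.2.4 that addresses another question, and one (staff time) lacks a data item in Section 6. That is three of seven, plus one Table 1 contrast (HRQoL) not carried into 8.2.4.

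**The case against.** The strongest reply is that the protocol does not confine itself to correlations. Table 1 names a group comparison for satisfaction and an arm contrast for quality of life, 8.2 says data are analysed by group, and a detailed plan is still to come. Section 8.2.4 does not call its list exhaustive, and the outcomes are exploratory. This stands to the extent that a missing model is no fault in a protocol. It does not remove the mismatch: the section that fixes the analysis of these outcomes names a different one from the objectives and Table 1. For adherence there is no specific arm comparison anywhere to fall back on.

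Four stronger readings are tempting but unsupported:

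- A reader might infer that EQ-5D-5L has no analysis. Table 1 names one; 8.2.4 merely fails to repeat it.
- A reader might infer that the trial cannot report on satisfaction or quality of life. Both are collected in both arms at three visits, so estimates remain available.
- A reader might take Table 1's single evaluation point for satisfaction as an error, since it is measured three times. Evaluating it just after the consultation is a legitimate choice.
- A reader might put a percentage on the understated staff time. That would rest wholly on an assumed preparation time.

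On staff time it can also be said that 8.4 commits the study to collecting preparation time and that the case report form, which is not shown, may already have the field. That is possible, but Section 6 and 9.2 as written say otherwise. The clash between the two tested sentences can be read as loose wording; it needs an edit, no more.

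**Conclusion.** The point holds as an inconsistency that should be corrected. Section 8.2.4 specifies correlations with anxiety where 2.2.2 asks for effects of the consultation, and it does not match the comparisons in Table 1. The gap is widest for adherence, narrower for satisfaction, and for quality of life only a failure to carry Table 1 forward. The omission of preparation time from Section 6 is the more pressing part, because it concerns data that may not be recoverable.

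The primary outcome and the sample size are unaffected. The conclusion on the analysis rests on the text alone; the simulation percentages depend on their assumed effect sizes and serve only as illustration. The conclusion on preparation time assumes that data collection follows Section 6, as 9.2 indicates.

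**What to change.** In 8.2.4:

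- Add between-arm estimates with 95% confidence intervals, without significance tests, for adherence and technical satisfaction. Report bladder filling only in patients to whom it applies, and keep the proviso in 4.3.4 that the adherence analysis depends on recruitment.
- Carry over the intervention-versus-control contrast for EQ-5D-5L from Table 1.
- Use the baseline values already collected for satisfaction and EQ-5D-5L. Model forms can be left to the statistical analysis plan.
- Keep the correlations with anxiety as descriptive, and reword the second sentence so that it agrees with the first that nothing is tested for significance.

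In 6.5, add preparation time to the intervention data list and make sure the case report form has the field. This should be done as early as possible, since consultations held without the field would lack a contemporaneous record.

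The cost is a short protocol amendment, one case report form field with a brief entry per consultation, and a little extra analysis. No additional patient data are needed.
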